#### 7.4.10.3 Chest X-ray

A chest X-ray (anterior-posterior and left lateral views) will be assessed during the Screening period to exclude subjects with relevant pulmonary diseases. Subjects will be referred to a

Data and information contained in this document are considered to constitute trade secrets and confidential commercial information, and the legal protections provided to such trade secrets and confidential information are hereby claimed under the provisions of applicable law. No part of this document may be publicly disclosed without the written consent of Philip Morris Products S.A.

radiology facility for this procedure. No new examination is required if the subject can present a chest X-ray with anterior-posterior and left lateral views at the Screening Visit which is not older than 6 months.

## 7.5 Biomarker Assessment

All bioanalytical assays and laboratory assessments ([Section 7.6](#)) will be carried out using validated methods. The bioanalytical methods used will be documented in the Bioanalytical Report. A list of laboratories is provided in [Appendix 2](#).

The start time of the use of each product has to be documented on single use days (Day 1 and Day 3).

Precautions should be taken during blood sampling and processing to prevent the contamination of samples with environmental nicotine or CO.

### 7.5.1 Biomarker of Exposure

#### 7.5.1.1 Biomarkers of Exposure to CO and COHb

COHb measured in blood and exhaled CO will be investigated as a measure of exposure to CO. The CO breath test will also serve as a measure of compliance in subjects using NNS as well as on the wash-out days in all subjects.

##### CO Breath Test

CO in exhaled breath will be measured using the Micro+™ Smokerlyzer® device (Bedfont Limited, Rochester, United Kingdom, see [Appendix 6](#)). The test will be performed for all subjects including the subjects using the NNS.

A CO breath test will be conducted once on Day -1 and Day 4:

On Day 0, Day 1, Day 2, Day 3, four CO breath tests will be done per day. On Day 1 and Day 3, the first test per day will be performed within 15 minutes prior to  $T_0$  and then around 12:00 PM, 4:00 PM, and 8:00 PM. On the wash-out days (Day 0 and Day 2) it will be conducted around 8:00 AM, 12:00 PM, 4:00 PM and 8:00 PM.

##### Carboxyhemoglobin

Tests for COHb measurement will be performed at a local laboratory.

Blood samples will be taken as follows at Day 1 and Day 3:

A total of five blood samples will be taken. The first sample will be taken within 15 minutes prior to using the first product ( $T_0$ ). Thereafter, the sampling times in relation to  $T_0$  are at 15 minutes, 60 minutes, 4 hours and 12 hours post- $T_0$ .

#### 7.5.1.2 Biomarkers of Exposure to Nicotine

Blood samples to measure nicotine in plasma will be taken as follows:

Single Use on Day 1 and Day 3:

A total of 16 blood samples will be taken for a 24-hour profile (Day 1 and Day 3). The first blood sample will be taken within 15 minutes prior to the single use ( $T_0$ ). Times of sampling are thereafter in relation to  $T_0$ :  $T_1$  after 2 minutes,  $T_2$  after 4 minutes,  $T_3$  after 6 minutes,  $T_4$  after 8 minutes,  $T_5$  after 10 minutes,  $T_6$  after 15 minutes,  $T_7$  after 30 minutes,  $T_8$  after 45 minutes,  $T_9$  after 60 minutes,  $T_{10}$  after 2 hours,  $T_{11}$  after 4 hours,  $T_{12}$  after 6 hours,  $T_{13}$  after 9 hours,  $T_{14}$  after 12 hours and  $T_{15}$  after 24 hours (this sample will be drawn during the day following product use, i.e., wash-out).

#### 7.5.2 CYP2A6 Activity

CYP2A6 activity will be measured in plasma on Day -1 ([Jacob et al, 2011](#)). CYP2A6 activity drives the metabolism of nicotine to cotinine and subsequent metabolites. In this study the CYP2A6 activity will be measured using the metabolic molar ratio of *trans*-3'-hydroxycotinine/cotinine.

### 7.6 Laboratory Assessments

A list of laboratories is provided in [Appendix 2](#).

#### 7.6.1 Clinical Chemistry, Haematology, and Urine Analysis for Safety Panel

Haematology, clinical chemistry and urine analysis for the safety panel will be measured at Screening, at day of Admission (Day -1) and at the Day of Discharge (Day 4). Tests will be conducted at a local laboratory or the site. Blood will be taken after no less than the 10 hours of fasting (see [Section 6.6.2](#)). The urine test will be performed semi-quantitatively as urine dip-stick test at the site. Parameters to be measured are listed in [Table 3](#).

**Table 3. Clinical Laboratory Parameters for Safety Panel**

Haematology	Clinical chemistry	Urine analysis
- Haematocrit	- Albumin	- pH
- Haemoglobin	- Total protein	- Bilirubin
- Mean corpuscular haemoglobin	- Alkaline phosphatase	- Glucose
- Mean corpuscular haemoglobin concentration	- Alanine aminotransferase	- Nitrite
- Mean corpuscular volume	- Aspartate aminotransferase	- Red blood cell traces
- Platelet count	- Blood urea nitrogen	- Protein
- Red blood cell count	- Creatinine	- Specific gravity
- White blood cell (count) (WBC)	- Gamma-glutamyl transferase	
- Differential WBC count:	- Fasting glucose	
• Neutrophils	- Lactate dehydrogenase	
• Basophils	- Potassium	
• Eosinophils	- Sodium	
• Lymphocytes	- Total bilirubin	
• Monocytes	- Direct bilirubin	
	- Total cholesterol	
	- Triglycerides	

### 7.6.2 Serology

A test for Hepatitis B surface antigen, Hepatitis C virus and HIV (anti-HIV1/2 and p24 antigen) will be done at Screening. In case of positive results, the subject will be referred to appropriate medical care.

### 7.6.3 Urine Drug Screen

A urine drug screen will be performed at the site at the Screening Visit and at the day of Admission. The urine will be screened for amphetamines, barbiturates, benzodiazepines, cannabinoids, cocaine, and opiates.

Data and information contained in this document are considered to constitute trade secrets and confidential commercial information, and the legal protections provided to such trade secrets and confidential information are hereby claimed under the provisions of applicable law. No part of this document may be publicly disclosed without the written consent of Philip Morris Products S.A.

#### 7.6.4 Urine Cotinine Screening

A urine dip-stick cotinine test will be performed at Screening and at Admission to the clinic in order to confirm the subject's smoking status. The test must detect cotinine with a cotinine of  $\geq 200$  ng/mL, (i.e., One-Step Cotinine Test 008A086, Ultimed, Belgium).

#### 7.6.5 Alcohol Breath Test

Subjects will undertake a breath alcohol test at the Screening Visit and at Admission to the clinic using a newly calibrated alcometer device (e.g., Alcotest 7410 Plus, Dräger).

#### 7.6.6 Urine Pregnancy Testing

All female subjects will have pregnancy testing at the Screening Visit, at Admission to the clinic, and at the Day of Discharge (Day 4). Female subjects with a positive pregnancy test at the Screening Visit or on Day -1 cannot be enrolled and are considered a screening failure. Pregnancy in such subjects will not be followed up as no exposure to the THS 2.2 will have occurred. Product test at Admission must be done only in female subjects with a negative pregnancy test. In any case of a positive pregnancy test, the Investigator will inform the subject about the risks associated with smoking during pregnancy. In the event of unclear urine pregnancy test in peri-menopausal women, absence of pregnancy should be confirmed by a serum follicle stimulating hormone level  $>20$  IU/l.

All pregnancies detected during the study must be reported and handled as described in [Section 8.5](#).

### 7.7 Sample Handling, Storage, and Shipment

Participating laboratories for blood samples testing will be decided prior to investigator meeting and site initiation. Safety laboratory samples will be tested at a local laboratory (see [Appendix 2](#)). The urine dipstick for the safety laboratory, urine drug screen, urine pregnancy tests and urine cotinine tests will be done by the site personnel at the site. The tests will be provided by the sites.

Detailed procedures for handling of samples are described in the separate sample handling manual (SHM). Safety laboratory samples will be destroyed as by the laboratories standard procedures. All other samples will be destroyed once the CSR has been finalized. The facility/-ies at which the samples are stored will be informed in writing by the Sponsor when destruction of the samples shall be performed.

#### Blood samples

Data and information contained in this document are considered to constitute trade secrets and confidential commercial information, and the legal protections provided to such trade secrets and confidential information are hereby claimed under the provisions of applicable law. No part of this document may be publicly disclosed without the written consent of Philip Morris Products S.A.

Blood samples will be drawn by qualified and trained site personnel. Subjects should be in a seated position during blood collection. In total, around 260 mL will be drawn for this study including planned assessments, safety, and repeated analysis for safety. The required aliquots and volumes for assessments of blood/plasma parameters and tests are summarized in the SHM.

#### Urine samples

Spot urine samples will be taken for urine drug screen, cotinine screen, pregnancy tests and safety urinalysis.

### **7.8 Questionnaires**

The subject questionnaires and the VAS will be entered by the subject directly in the electronic patient reported outcomes device or in paper copy. The questionnaires and the VAS will be reviewed for completeness by the study site staff and subjects will be requested to complete any missing information.

Symptoms or worsening of symptoms as documented on any of the questionnaires or the VAS do not need to be documented as AEs because the questionnaire and the VAS will be analysed as part of the report. However, it is at the discretion of the Investigator to document such symptoms also as AEs. The main source for AE collection will be the face-to-face interview between the subject and site staff using, open, non-directive questions (see section [Section 8](#)).

#### **7.8.1 Fagerström Test for Nicotine Dependence (revised version)**

Potential nicotine dependence will be assessed at Screening using the FTND in its revised version ([Heatherton et al, 1991](#)), as updated in 2012 ([Fagerström et al, 2012](#)).

The questionnaire consists of six questions which have to be answered by the subject himself/herself. The scores obtained on the test permit the classification of nicotine dependence into three levels: Mild (0 to 3 points); Moderate (4 to 6 points); Severe (7 to 10 points) ([Fagerström et al, 2012](#)).

#### **7.8.2 Assessment of Cough**

Subjects will be asked if they have experienced a regular need to cough e.g. coughing several times in the last 24 hours prior to assessment. If the answer is 'yes', they will be asked to complete a VAS, three Likert scales and an open question also assessing the previous 24 hours.

Data and information contained in this document are considered to constitute trade secrets and confidential commercial information, and the legal protections provided to such trade secrets and confidential information are hereby claimed under the provisions of applicable law. No part of this document may be publicly disclosed without the written consent of Philip Morris Products S.A.

The VAS will assess how bothersome cough is to the subject ranging from 'not bothering me at all' to 'extremely bothersome'.

Furthermore, subjects will be asked to assess the intensity and frequency of cough and the amount of sputum production on Likert scales:

- The intensity of cough will be assessed on a 5-point Likert scale ranging from 1 to 5: 1 = very mild; 2 = mild; 3 = moderate; 4 = severe; 5 = very severe.
- The frequency of cough will be assessed on a 5-point Likert scale ranging from 1 to 5: 1 = rarely; 2 = sometimes; 3 = fairly often; 4 = often; 5 = almost always.
- The amount of sputum production will be assessed on a 4-point Likert scale ranging from 0 to 3: 0 = no sputum; 1 = a moderate amount of sputum; 2 = a larger amount of sputum; 3 = a very large amount of sputum.

Finally, subjects will be asked with an open question if there are any other important observations that they would like to share with the staff about their coughing.

Assessments will be done on a daily basis from Day 0 to Day 4. On Day 2 and Day 4, questionnaire must be asked 24 hours after T0 of Day 1 and after 24 hours minus 5 minutes after T0 of Day 3.

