#### **4.4 Appropriateness of Measurements**

The laboratory measures to be utilized in this study were selected based on the following criteria: 1) the availability of a validated analytical method, and 2) measure is known to be directly or indirectly affected by smoking; 3) measure is readily reversible after smoking cessation, 4) timeframe of reversibility of measure in the perspective of the study duration, 5) practicality/acceptability by subjects, and 6) robustness (rapid, simple, accurate).

All questionnaires utilized for this study, except the cough and socio-economic status questionnaires, are available as validated questionnaires.

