#### 12.6.5 Safety Endpoints

In general, all safety data will be listed and tabulated on the safety population by sequence, using the approach described in [Section 12.1.3](#). Safety variables collected during exposure periods will also be reported by product exposure.

AE data will serve as the primary assessment of safety. Other safety variables monitored in this study include: respiratory symptoms (cough assessment VAS and Likert scales); vital signs (systolic and diastolic blood pressure, pulse rate, respiratory rate); spirometry; ECG data; clinical chemistry, haematology, and urine analysis safety panel; physical examination; and concomitant medication.

The number and percentage of subjects with AEs and SAEs will be tabulated by system organ class and preferred term. Summaries will also be presented for AEs leading to withdrawal, AEs leading to Death, AEs by relatedness to product exposure, AEs by severity, and laboratory AEs. Tabulations will be performed for both the number of subjects experiencing an event and the number of events. The number and percentage of device events and of subjects with device events will be tabulated by sequence.

Data and information contained in this document are considered to constitute trade secrets and confidential commercial information, and the legal protections provided to such trade secrets and confidential information are hereby claimed under the provisions of applicable law. No part of this document may be publicly disclosed without the written consent of Philip Morris Products S.A.

The number and percentage of subjects with clinical findings will be tabulated by sequence for laboratory parameters. Shift tables showing change from baseline of clinical findings will be provided for ECGs, physical examinations, and laboratory parameters (both shifts in normal ranges and toxicity grades). Descriptive statistics will be summarized by visit and change from baseline for laboratory parameters, ECG, respiratory symptoms, and vital signs.

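### The sputum scale in Section 7.8.2 has no category between none and moderate, so a coughing subject with a small amount has no label that fits

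*Protocol*

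**What the plan says.** Protocol Section 7.8.2 first asks whether the subject has had a regular need to cough in the previous 24 hours. "If the answer is 'yes', they will be asked to complete a VAS, three Likert scales and an open question". One of the three scales is sputum: "The amount of sputum production will be assessed on a 4-point Likert scale ranging from 0 to 3", with the labels "0 = no sputum; 1 = a moderate amount of sputum; 2 = a larger amount of sputum; 3 = a very large amount of sputum". The intensity scale in the same list reads "1 = very mild; 2 = mild; 3 = moderate; 4 = severe; 5 = very severe".

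Four other sections bear on the item:

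- **Section 4.4, on validation:** "All questionnaires utilized for this study, except the cough and socio-economic status questionnaires, are available as validated questionnaires".
- **Section 7.8, on completeness:** site staff review the questionnaires and ask subjects to fill in missing answers. Symptoms recorded on them need not also be recorded as adverse events, because the questionnaires are analysed in the report. The investigator may still record them.
- **Sections 3.4 and 12.6.5, on use:** respiratory symptoms on the VAS and Likert scales are safety variables. Descriptive statistics are to be "summarized by visit and change from baseline for laboratory parameters, ECG, respiratory symptoms, and vital signs".
- **Section 12.1.2, on baseline:** the last available time point before first product use on Day 1.

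**The concern.** The lowest non-zero label already says moderate. A subject with a little sputum has to call it none or call it moderate. Different subjects may settle this differently, and so may one subject on different days. The count of subjects with any sputum, and a change between 0 and 1, then depend partly on how the label was read.

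This matters a little more because Section 7.8 lets the questionnaire stand in for adverse event recording of these symptoms. What the scale cannot register may not be captured in graded form elsewhere, and the lost detail cannot be recovered after collection.

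**Working it through.** No power or error-rate calculation applies. The check sets the labels side by side and traces what each true state can be recorded as.

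**Labels in Section 7.8.2**

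| Scale | Codes | Lowest non-zero label | Non-zero grades below moderate |
|---|---|---|---|
| Intensity of cough | 1 to 5 | very mild | 2 (very mild, mild) |
| Frequency of cough | 1 to 5 | rarely | not graded by that word; starts at the low end |
| Sputum amount | 0 to 3 | moderate | 0 |

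The sputum labels are identical in the Final 2.0 and Final 3.0 texts of the protocol, so this is not a slip in one printing. No other section gives a different scale.

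**Ways round the gap.** Under Section 7.8 a blank is not an intended answer. The open question can hold a remark about a small amount, but only as free text and not as a score.

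**What can be recorded.** The added-category column uses 0 = none, 1 = small, 2 = moderate, 3 = larger, 4 = very large.

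| True course | Present labels | Change shown | With the added category | Change shown |
|---|---|---|---|---|
| small, then small | 0→0, 1→1, 0→1 or 1→0 | 0, +1 or −1 | 1→1 | 0 |
| none, then small | 0→0 or 0→1 | 0 or +1 | 0→1 | +1 |
| small, then moderate | 0→1 or 1→1 | +1 or 0 | 1→2 | +1 |
| none, then moderate | 0→1 | +1 | 0→2 | +2 |

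With the present labels, each course that involves a small amount can be recorded in more than one way, and none-to-small can look the same as none-to-moderate. With the added category, each course has one fitting record.

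**Step size.** One point is 1/3 of the range on the 0-3 scale and 1/4 on a 0-4 scale. On a four-point scale relabelled none, small, moderate, large, one point is still 1/3. The gain is therefore a clear rule for choosing the lowest non-zero category, and only incidentally a finer step.

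**Timing of the assessments** (Sections 6.2.1 and 7.8.2, Tables 6 to 9). The item looks back 24 hours.

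- Day 0 follows a day of ad libitum smoking.
- Day 1 and Day 3 are assessed before product use and look back over washout.
- Only Day 2 and Day 4 look back over a single product use.

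**The case against.** The case for leaving the scale alone has real content.

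- **Order is preserved.** Category 1 is the lowest non-zero choice, and a subject who reads it the same way throughout does so for both products in the crossover. This stands in part. Consistent reading prevents false changes, but it still cannot separate small from none or small from moderate, and nothing in the protocol tells subjects which reading to adopt.
- **Other channels exist.** The VAS, the intensity and frequency scales and the open question sit alongside, and Section 12.6.5 makes adverse events the primary safety assessment. This stands as a limit on importance. None of the other scales grades sputum amount.
- **The affected comparison is narrow.** A direct change in score needs a yes to the cough question at baseline and again later. How a no is scored, and whether the item is summarised as numbers or as category counts, may be settled in the SAP, which is not shown. This stands.

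A reader might also infer three stronger things that the protocol does not support:

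- **That the defect lies in a small change showing as a full point, a third of the range.** Any four-category scale has that step, including a relabelled one.
- **That small amounts are the likely answer in healthy smokers after one product use.** No sputum frequency is given, and only two of the five daily assessments look back over a single use.
- **That the wording is free to change because the questionnaire is not validated.** Section 4.4 removes one reason for keeping the labels but does not show that no other exists. Section 12.2 cites a preceding PK study in the programme, and its cough form, if any, is not shown.

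**Conclusion.** The gap is certain as printed: the four labels hold nothing between none and moderate, and a small amount is necessarily misdescribed. The result is an ambiguous none/any boundary in one descriptive safety item.

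The number of subjects affected cannot be stated. It depends on how many report a regular need to cough and how many of those have small amounts, and the protocol gives neither figure. The conclusion also assumes that the form handed to subjects carries the same labels as Section 7.8.2; the form is not among the documents.

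The PK endpoints, the THS 2.2 versus NNS tests and the sample size of 62 are untouched. This is an inexpensive improvement and no threat to any study conclusion.

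**What to change.** Check the electronic or paper form. If it carries the printed labels, then before the first subject change the item to five points: 0 = no sputum, 1 = a small amount, 2 = a moderate amount, 3 = a larger amount, 4 = a very large amount. Amend the description in Section 7.8.2 from four points and 0-3 to five points and 0-4. The planned descriptive summaries stay as they are.

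The cost is a text change to the form and the coding list, a range of 0-4, and loss of direct comparability with any data collected under the present labels.

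The alternative is to keep four points and relabel 1 to 3 as small, moderate and large. This preserves the 0-3 range but loses the split between the two highest categories, and scores would still not be comparable with data under the present labels. Adding a category keeps the detail at the heavy end of a safety item and is the better choice unless four points are required for another reason.

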### 7.8.3      **Modified Cigarette Evaluation Questionnaire (modified version)**

Product evaluation will be assessed using the MCEQ ([Cappelleri et al, 2007](#)). The MCEQ assesses the degree to which subjects experience the reinforcing effects of smoking, by measuring:

- Smoking satisfaction (satisfying, tastes good, enjoy smoking).
- Psychological rewards (calms down, more awake, less irritable, helps concentrate, reduces hunger).
- Aversion (dizziness, nauseous).
- Enjoyment of respiratory tract sensations (single-item assessment).
- Craving reduction (single-item assessment).

Data and information contained in this document are considered to constitute trade secrets and confidential commercial information, and the legal protections provided to such trade secrets and confidential information are hereby claimed under the provisions of applicable law. No part of this document may be publicly disclosed without the written consent of Philip Morris Products S.A.

This questionnaire will only be completed by the subjects, who use the THS 2.2 or smoke CC during the study in sequence 1 and 2. The MCEQ will be completed by subjects on Day 1 and Day 3.

